### **10.3.10. Other events requiring reporting**

#### *10.3.10.1. Overdose*

Use of durvalumab or tremelimumab in doses in excess of that specified in the protocol is considered to be an overdose. There is currently no specific treatment in the event of overdose of durvalumab or tremelimumab, and possible symptoms of overdose are not established.

- An overdose with associated AEs will be recorded as the AE diagnosis or symptoms in the relevant AE modules of the eCRF and in the Overdose eCRF module.
- An overdose without associated symptoms will only be reported in the Overdose eCRF module.

If an overdose of an AstraZeneca IP occurs in the course of the study, then the Investigator or other site personnel will inform appropriate sponsor representatives immediately, or **no later than 24 hours** of when he or she becomes aware of it.

The designated sponsor representative will work with the Investigator to ensure that all relevant information is provided.

For overdoses associated with an SAE, the standard reporting timelines apply, see Section 10.3.10.1. For other overdoses, reporting must occur within 30 days.

#### *10.3.10.2. Pregnancy*

All pregnancies and outcomes of pregnancy should be reported to the sponsor except for:

- Pregnancy discovered before the study patient has received any study drugs.
- Pregnancy of a female partner of male patient, providing there is no restriction of male patient fathering a child.

### **10.3.11. Maternal exposure**

If a patient becomes pregnant during the course of the study, the IPs should be discontinued immediately.

Pregnancy itself is not regarded as an AE unless there is a suspicion that the IP under study may have interfered with the effectiveness of a contraceptive medication. Congenital abnormalities or birth defects and spontaneous miscarriages should be

reported and handled as SAEs. Elective abortions without complications should not be handled as AEs. The outcome of all pregnancies (spontaneous miscarriage, elective termination, ectopic pregnancy, normal birth, or congenital abnormality) should be followed up and documented even if the patient was discontinued from the study.

If any pregnancy occurs in the course of the study, then the Investigator or other site personnel should inform the appropriate sponsor representatives within 1 day, i.e., immediately, but **no later than 24 hours** of when he or she becomes aware of it.

The designated sponsor representative will work with the Investigator to ensure that all relevant information is provided within 1 to 5 calendar days for SAEs and within 30 days for all other pregnancies.

The same timelines apply when outcome information is available.

#### **10.3.12. Paternal exposure**

Male patients should refrain from fathering a child or donating sperm during the study and for 180 days after the last dose of durvalumab + tremelimumab combination therapy or 90 days after the last dose of durvalumab monotherapy, whichever is the longer time period.

Pregnancy of the patient's partner is not considered to be an AE. However, the outcome of all pregnancies (spontaneous miscarriage, elective termination, ectopic pregnancy, normal birth, or congenital abnormality) occurring from the date of the first dose until 180 days after the last dose of durvalumab + tremelimumab combination therapy or 90 days after the last dose of durvalumab monotherapy, whichever is the longer time period should, if possible, be followed up and documented.

Where a report of pregnancy is received, prior to obtaining information about the pregnancy, the Investigator must obtain the consent of the patient's partner. Therefore, the local study team should adopt the generic ICF template in line with local procedures and submit it to the relevant Ethics Committees (ECs) prior to use.

#### **10.4. Medication error**

For the purposes of this clinical study a medication error is an unintended failure or mistake in the treatment process for an AstraZeneca study drug that either causes harm to the patient or has the potential to cause harm to the patient.

A medication error is not lack of efficacy of the drug, but rather a human or process related failure while the drug is in control of the study site staff or patient.

Medication error includes situations where an error.

- occurred
- was identified and intercepted before the patient received the drug
- did not occur, but circumstances were recognized that could have led to an error

Examples of events to be reported in clinical studies as medication errors:

- Drug name confusion
- Dispensing error e.g. medication prepared incorrectly, even if it was not actually given to the patient
- Drug not administered as indicated, for example, wrong route or wrong site of administration
- Drug not taken as indicated e.g. tablet dissolved in water when it should be taken as a solid tablet
- Drug not stored as instructed e.g. kept in the fridge when it should be at room temperature
- Wrong patient received the medication (excluding IVRS/IWRS errors)
- Wrong drug administered to patient (excluding IVRS/IWRS errors)
- Examples of events that **do not** require reporting as medication errors in clinical studies:
  - Errors related to or resulting from IVRS/IWRS - including those which lead to one of the above listed events that would otherwise have been a medication error
  - Patient accidentally missed drug dose (s) e.g. forgot to take medication
  - Accidental overdose (will be captured as an overdose)
  - Patient failed to return unused medication or empty packaging
  - Errors related to background and rescue medication, or standard of care medication in open label studies, even if an AZ product

Medication errors are not regarded as AEs but AEs may occur as a consequence of the medication error.

If a medication error occurs in the course of the study, then the Investigator or other site personnel informs the appropriate sponsor representatives within 1 day i.e., immediately but **no later than 24 hours** of when he or she becomes aware of it.

The designated sponsor representative works with the Investigator to ensure that all relevant information is completed within 1 or 5 calendar days if there is an SAE associated with the medication error (see Section 10.3.10) and within 30 days for all other medication errors.

## 11. STATISTICAL METHODS AND SAMPLE SIZE DETERMINATION

### 11.1. Description of analysis sets

#### 11.1.1. Safety analysis set

The safety analysis set will include all patients who receive at least 1 dose of study treatment. The safety analysis set will be the primary population for evaluating treatment administration/compliance and safety.

#### 11.1.2. Efficacy analysis set

The efficacy analysis will be a *per protocol analysis*. The efficacy analysis set will include all patients who receive at least 2 cycles of durvalumab and 3 weeks of radiotherapy. The efficacy analysis set will be the primary population for evaluating treatment efficacy.

Additionally, intention to treat analysis will be performed for efficacy data.

### 11.2. Methods of statistical analyses

#### 11.2.1. Safety analyses

Safety analysis will be performed weekly during the length of the treatment and every three months later (late toxicity associated with radiotherapy). Toxicities will be graded according to NCI CTCAE, Version 4.03 and RTOG/EORTC grading system.

#### 11.2.2. Efficacy analyses and exploratory analyses

Table 8. *Efficacy analyses and exploratory analyses*

Objectives	Variable	Analysis	Clinical factors	Analysis population
Primary: efficacy of durvalumab plus tremelimumab with concurrent radiotherapy in terms of pathological response rate	Pathological response rate	1. Proportion estimation with a 95% confidence interval 2. Simon two stage decision rule 3. Logistic regression with clinical factors	Tumour size Tumour localization Histology Biomarkers	Per protocol
Secondary 1a: bladder preservation.	Rate of bladder preserved	1. Proportion estimation with a 95% confidence interval 2. Logistic regression with clinical factors	Tumour size Tumour localization Histology Biomarkers	Per protocol
Secondary 1b: bladder preservation.	Rate of immediate and late salvage cystectomies.	1. Proportion estimation with a 95% confidence interval 2. Logistic regression with clinical factors	Tumour size Tumour localization Histology Biomarkers	Per protocol

Secondary 1c: bladder preservation.	Time from start of immunotherapy to the date of recurrence of muscle invasive bladder carcinoma or metastases.	Kaplan Meier estimation of survival with a 95 % confidence interval	Not applicable	Per protocol
Secondary 1d: Overall survival	Time from treatment start to exitus.	Kaplan Meier estimation of survival with a 95 % confidence interval		Per protocol
Secondary 1.3: Progression free survival	Time from treatment start to tumour relapse or distant progression.	Kaplan Meier estimation of survival with a 95 % confidence interval		Per protocol
Secondary 2: Safety profile and tolerability of combination	CTCAE V4.03	1. Frequency table with adverse events, grades and relationship to study drugs and to radiotherapy treatment 2. Frequency table with severe toxicity.	Durvalumab cumulative dose, tremelimumab cumulative dose, radiotherapy treatment constraints (dose in risk organs).	Safety population
Secondary 3: To evaluate the long term functionalism and late sequel of the treatment in the preserved bladders.	Bladder control scale	Repeated measures analysis		Per protocol
Exploratory 1: Biomarkers and pathological response rate	Biomarkers and pathological response rate	Logistic regression in which response or not is the response and baseline biomarkers are factors to be studied	Biomarkers	Per protocol
Exploratory 2: Biomarkers evolution between baseline and surgery time	Biomarkers evaluated at baseline vs surgery evaluation	Paired t-test or Wilcoxon Signed Rank Test (depending on the nature of variables)		Per protocol

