#### **4.4. Withdrawal of patients from study treatment**

An individual patient will not receive any further investigational product if any of the following occurs:

- An individual patient will not receive any further durvalumab + tremelimumab combination therapy.
- Patient will not receive tremelimumab monotherapy in any case.
- Withdrawal of consent or lost to follow-up.
- Adverse event that, in the opinion of the investigator or the sponsor, contraindicates further dosing.
- Any AE that meets criteria for discontinuation, as defined in Section 10.
- Patient is determined to have met one or more of the exclusion criteria for study participation at study entry and continuing investigational therapy might constitute a safety risk.
- Consumption of illicit drugs or other substances by the patient which, at the discretion of the investigator, may reasonably contribute to the toxicity or otherwise, interfere in some with the results.
- Pregnancy (proof of beta-HCG compatible with pregnancy, communicating pregnancy as a serious adverse event), or intent to become pregnant.
- Grade  $\geq 3$  infusion reaction.
- Request to discontinue treatment by the patient or a legal representative.
- At the specific request of the sponsor and / or research coordinators of the trial.
- Patient noncompliance that, in the opinion of the investigator or sponsor, warrants withdrawal; e.g., refusal to adhere to scheduled visits.
- Initiation of alternative anticancer therapy including another investigational agent.
- Development of a secondary malignant tumor requiring treatment.
- Confirmation of PD and investigator determination that the patient is no longer benefiting from treatment with durvalumab + tremelimumab. Patients who are permanently discontinued from further receipt of investigational product, regardless of the reason (withdrawal of consent, due to an AE, other), will be identified as having permanently discontinued treatment

Patients who are permanently discontinued from receiving investigational product will be followed for safety per Section 10 and Appendix 1, including the collection of any protocol-specified blood specimens, unless consent is withdrawn or the patient is lost to follow-up or enrolled in another clinical study. All patients will be followed for survival. Patients who decline to return to the site for evaluations will be offered follow-up by phone every 3 months as an alternative.

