## **5.5 Dose and treatment regimens**

### **5.5.1. Treatment regimens**

#### **Durvalumab + tremelimumab combination therapy**

All patients will receive durvalumab (MEDI4736) (1500mg Q4W) in combination with tremelimumab (75 mg IV Q4W) for up to 3 doses/cycles each, unless there is unacceptable toxicity, withdrawal of consent, or another discontinuation criterion is met. If a patient's weight falls to 30kg or below the patient should receive weight-based dosing equivalent to 20 mg/kg of durvalumab Q4W and 1mg/kg tremelimumab Q4W until the weight improves to >30 kg, at which point the patient should start receiving the fixed dosing of durvalumab 1500mg plus tremelimumab 75 mg Q4W.

Tremelimumab will be administered first; the durvalumab (MEDI4736) infusion will start approximately 1 hour (maximum 2 hours) after the end of the tremelimumab infusion. Standard infusion time for each is one hour. If there are interruptions during infusion, the total allowed infusion time for each should not exceed 8 hours at room temperature. If

there are no clinically significant concerns after the first cycle, then, at the discretion of the Investigator, all other cycles of durvalumab (MEDI4736) can be given immediately after the tremelimumab infusion has finished.

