#### **6.1.2. Durvalumab and tremelimumab**

Guidelines for the management of immune-mediated reactions, infusion-related reactions, and non-immune-mediated reactions for durvalumab monotherapy and durvalumab + tremelimumab are provided in the Dosing Modification and Toxicity Management Guidelines in Appendix 1. Patients should be thoroughly evaluated and appropriate efforts should be made to rule out neoplastic, infectious, metabolic, toxin, or other etiologic causes of the imAE. Serologic, immunologic, and histologic (biopsy) data, as appropriate, should be used to support an imAE diagnosis. In the absence of a clear alternative etiology, events should be considered potentially immune related.

In addition, there are certain circumstances in which durvalumab and tremelimumab should be permanently discontinued (see Section 4.4 of this protocol and the Dosing Modification and Toxicity Management Guidelines in Appendix 1).

Following the first dose of IP, subsequent administration of durvalumab and tremelimumab can be modified based on toxicities observed as described in the Dosing Modification and Toxicity Management Guidelines in Appendix 1. These guidelines have been prepared by the Sponsor to assist the Investigator in the exercise of his/her clinical judgment in treating these types of toxicities. These guidelines apply to AEs considered causally related to durvalumab monotherapy and the durvalumab + tremelimumab regimen by the reporting investigator.

**Dose reductions are not permitted.** In case of doubt, the Investigator should consult with the Study Physician. In case of severe grade 3-4 toxicity, the possibility to discontinue tremelimumab, following the administration of durvalumab alone concurrently with radiotherapy, when the toxicity will recover, should be considered.

It is planned to replace those patients who interrupt the trial in advance (without having completed 12 weeks of treatment) and have not presented dose-limiting toxicity. Patients who have not been taking durvalumab and tremelimumab for more than 21 days or who discontinue treatment with radiotherapy for more than 2 weeks will also be replaced.

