
---

Grade 3 Depending on the individual toxicity, study drug/study regimen may be permanently discontinued. Please refer to guidelines below.
 
Grade 4 Permanently discontinue study drug/study regimen.
 
Note: For asymptomatic amylase or lipase levels of <math>>2.0 \times \text{ULN}</math>, hold study drug/study regimen, and if complete work up shows no evidence of pancreatitis, study drug/study regimen may be continued or resumed.
 
Note: Study drug/study regimen should be permanently discontinued in Grade 3 events with high likelihood for morbidity and/or mortality – e.g., myocarditis, or other similar events even if they are not currently noted in the guidelines. Similarly, consider whether study drug/study regimen should be permanently discontinued in Grade 2 events with high likelihood for morbidity and/or mortality – e.g., myocarditis, or other similar events even if they are not currently noted in the guidelines – when they do not rapidly improve to Grade <math><1</math> upon treatment with systemic steroids and following full taper
 
Note: There are some exceptions to permanent discontinuation of study drug for Grade 4 events (i.e., hyperthyroidism, hypothyroidism, Type 1 diabetes mellitus).
	
 
– More potent immunosuppressives such as TNF inhibitors (e.g., infliximab; also refer to the individual sections of the imAEs for specific type of immunosuppressive) should be considered for events not responding to systemic steroids.
 
– Progression to use of more potent immunosuppressives should proceed more rapidly in events with high likelihood for morbidity and/or mortality – e.g., myocarditis, or other similar events even if they are not currently noted in the guidelines – when these events are not responding to systemic steroids.
 
– With long-term steroid and other immunosuppressive use, consider need for Pneumocystis jirovecii pneumonia (PJP, formerly known as Pneumocystis carinii pneumonia) prophylaxis, gastrointestinal protection, and glucose monitoring.
 
– Discontinuation of study drug/study regimen is not mandated for Grade 3/Grade 4 inflammatory reactions attributed to local tumor response (e.g., inflammatory reaction at sites of metastatic disease and lymph nodes). Continuation of study drug/study regimen in this situation should be based upon a benefit-risk analysis for that patient.
 

---	--

---

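### A breakdown of adverse events by total durvalumab and tremelimumab dose, which Table 8 implies, is open to reverse causation because toxicity is itself a reason to miss infusions

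*Combined protocol and SAP*

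**What the plan says.** Table 8, row Secondary 2, covers the safety profile in the safety population. Its analysis column names two outputs: "Frequency table with adverse events, grades and relationship to study drugs and to radiotherapy treatment", and a frequency table of severe toxicity. Its clinical-factors column reads "Durvalumab cumulative dose, tremelimumab cumulative dose, radiotherapy treatment constraints (dose in risk organs". Nothing says when cumulative dose is measured or how it enters the tables.

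The dosing rules that determine cumulative dose are:

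- Protocol 5.5.1: "All patients will receive durvalumab (MEDI4736) (1500mg Q4W) in combination with tremelimumab (75 mg IV Q4W) for up to 3 doses/cycles each", with exceptions for unacceptable toxicity, withdrawn consent or another discontinuation criterion.
- Protocol 6.1.2: "Dose reductions are not permitted". The same section adds, "In case of severe grade 3-4 toxicity, the possibility to discontinue tremelimumab", while continuing durvalumab, should be considered.
- Protocol 4.4 ends treatment for, among other reasons, an "Adverse event that, in the opinion of the investigator or the sponsor, contraindicates further dosing".
- Appendix 1, General Considerations, instructs for Grade 4 immune-mediated events: "Permanently discontinue study drug/study regimen". It lists some exceptions.

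The SAP's end-of-treatment shell (Table 39) has three categories: intolerable toxicity, an unrelated adverse event, and completion. The safety set needs only one dose (protocol 11.1.1), so early stoppers remain in it.

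**The concern.** Every patient is planned the same three infusions of the same size, so total dose carries no planned contrast. Apart from the rule for body weight of 30 kg or less, it varies only with the number of infusions given. Adverse events are one route to a missed infusion, and in Table 39 they are the only listed route to an early end. A patient whose severe event ended treatment after one or two infusions falls into the low-dose group because of that event.

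A table of adverse events by total dose would then tend to show more toxicity at lower dose whatever the true relation. For a new combination given with radiotherapy, where safety is a secondary objective, that reading would be falsely reassuring about additional doses. The plan contains no landmark, time-dependent or dose-before-onset handling that would prevent it.

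**Working it through.** The plan gives no figure for this point, so there is none to reproduce.

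**What total dose can be.** The maxima are 3 × 1500 = 4500 mg durvalumab and 3 × 75 = 225 mg tremelimumab. Without reductions, total dose is the number of infusions times a constant. SAP section 3.1 states that all 32 patients had at least two durvalumab doses, so durvalumab takes two values, 3000 or 4500 mg. A breakdown by dose is then a comparison of patients who stopped before dose 3 with patients who completed.

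**Model with no dose effect.** None of these rates is in the documents; they are assumptions. Let *h* be the risk of severe toxicity in each cycle, *s* the share of those events that stop the drug, and *o* the chance per cycle that anyone not so stopped leaves for another reason.

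- Stop per cycle: w = hs + (1 − hs)o
- Fewer than 3 doses: 1 − (1 − w)²
- Stop in a cycle with toxicity in that same cycle: v = h[s + (1 − s)o]
- Toxicity in a completed cycle, given continuation: c = h(1 − s)/(1 − hs)
- Toxic, given 3 doses: 1 − (1 − c)²(1 − h)
- Toxic and fewer than 3 doses: v + (1 − w)[cw + (1 − c)v]

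*Middle setting, h = 0.13, s = 0.8, o = 0.05.*

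- hs = 0.104; w = 0.104 + 0.896 × 0.05 = 0.1488
- Fewer than 3 doses: 1 − 0.8512² = 27.5%
- v = 0.13 × 0.81 = 0.1053; c = 0.026/0.896 = 0.0290
- Toxic and fewer than 3: 0.1053 + 0.8512 × (0.0290 × 0.1488 + 0.9710 × 0.1053) = 0.196
- Toxic given fewer than 3: 0.196/0.2755 = **71%**
- Toxic given 3: 1 − 0.9710² × 0.87 = **18%**
- Share of shortfalls caused by toxicity: 0.104/0.1488 = 70%

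*Lighter setting, h = 0.07, s = 0.5, o = 0.02.*

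- w = 0.035 + 0.965 × 0.02 = 0.0543; fewer than 3 doses: 1 − 0.9457² = 10.6%
- v = 0.07 × 0.51 = 0.0357; c = 0.035/0.965 = 0.0363
- Toxic given fewer than 3: [0.0357 + 0.9457 × (0.0363 × 0.0543 + 0.9637 × 0.0357)]/0.1057 = **66%**
- Toxic given 3: 1 − 0.9637² × 0.93 = **14%**

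**Range.** I took h = 7, 13, 20%; s = 50, 80, 100%; o = 0, 2, 5, 10, 20%, which gives 45 settings.

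- *No dose effect:* the low-dose group looked more toxic in all 45. The narrowest contrasts came with frequent other stops and few toxicity stops, for example 20% against 14% at h = 7%, s = 50%, o = 20%.
- *Risk truly rising 1.5-fold with each dose:* the low-dose group still looked worse in 42 of 45 (76% against about 34% in the middle setting). The three exceptions all have s = 50% and o = 20%: essentially a tie at 23%, then 38% against 41% and 51% against 60%.
- *Share of shortfalls caused by toxicity, no dose effect:* above half in 32 of 45, ranging from 15% to 100%.

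**The case against.** Four points on the other side carry weight.

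- **No dose comparison is spelled out.** The Primary, 1a and 1b rows of Table 8 call for logistic regression on the clinical factors. The safety row names only frequency tables. The SAP safety shells (Tables 198 to 208) never cross toxicity with dose. Doses given, reasons for omission and reasons for ending treatment appear as separate description (Tables 27 to 35, 39 and 40). This stands: the breakdown is implied by the factor column and no current shell produces it. The factor remains in the protocol, though, and would be either run without a safeguard or dropped without explanation.
- **Severe toxicity does not always stop treatment.** Appendix 1 lets many Grade 3 events be held and resumed, and isolated hypothyroidism or type 1 diabetes need no interruption. Section 4.4 lists several stopping reasons unrelated to toxicity. This also stands, and is why *s* was taken as low as 50% and *o* as high as 20%.
- **The illustration may overstate early stopping.** Under the middle setting the chance that all 32 patients reach a second dose is 0.8512³² = 0.6%, which fits poorly with SAP section 3.1. Under the lighter setting it is 0.9457³² = 17%, and the contrast is still 66% against 14%.
- **Tremelimumab dose could differ by assignment.** If the run-in rule in section 11.2.3 is triggered, later patients receive one tremelimumab dose regardless of their own toxicity. That contrast would be informative and should not be discarded.

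A reader might infer that total dose falls mainly because of toxicity, or that the comparison is reversed by design. The documents support neither. They do not say which stopping reason dominates, and with enough other stops the sign can come out right.

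**Conclusion.** Total durvalumab and tremelimumab dose is not a sound explanatory factor for adverse events in this trial, because it is partly a consequence of them. The bias runs towards making lower dose look more toxic, and under the assumed rates it is usually large enough to hide or reverse a true increase of risk with dose. Its actual size is unknown: it depends on the rate of stopping for other reasons and on how many severe events end treatment, and the documents give neither. The conclusion also assumes that dose would be counted at the end of treatment, the ordinary reading of a cumulative dose that Table 8 leaves undefined.

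The point concerns one secondary safety row, in 32 patients, and an output that the SAP does not yet contain. It does not affect the primary endpoint or the planned adverse-event frequencies. It does not apply in the same way to the third factor, radiotherapy dose to organs at risk. I rate it a cheap improvement.

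**What to change.** In Table 8, Secondary 2:

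1. Replace total cumulative durvalumab and tremelimumab dose with dose received before onset of the event. Alternatively, report adverse events by cycle of onset (after dose 1, 2 and 3) over the patients who received that dose. State the onset window for each cycle, since doses are four weeks apart while adverse events are collected for 90 days after the last one.
2. Report total dose received and reasons for stopping as description only; the existing SAP shells already do this.
3. If the run-in rule changes tremelimumab for later patients, compare by assigned regimen and not by dose received.
4. Leave the organ-at-risk radiotherapy factor unchanged.

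Add the matching shell to the SAP safety section and label it descriptive. The cost is one edited protocol row and one extra by-cycle table, built from adverse-event start dates (protocol 10.3) and the week-by-week dosing records behind SAP sections 3.3.1 and 3.3.2. No new data are needed.
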